11. STUDY PROCEDURES

11.1. *Schedule of Assessments*

See Annex I.

11.2. *Baseline Visit (Days -28 to -1)*

At this visit the patient should be informed about all aspects of the study, including visits and tests to be performed. The patient will be asked to sign and date the informed consent form prior to performing any study procedure.

The informed consent form must be signed within 4 weeks before the start of the study medication. The original signed and dated informed consent form must be stored by the investigator in the patient's medical record and the patient must be provided with a copy.

The investigator will assess and confirm the eligibility of each patient, and all inclusion criteria must be met, but none of the exclusion criteria.

All the results of the tests undertaken during screening must be available before deciding whether a patient is eligible.

The specific baseline visit procedures envisaged by the protocol are as follows and must be performed within 28 days of initiating study treatment, or, failing that, screening must be repeated.

- Medical history.
- 12-lead ECG.
- Vital signs (blood pressure, heart rate, temperature, height and weight).
- A full physical examination.
- Complete blood test (See schedule of assessments, Annex I).
- NET markers (chromogranin A, enolase 1 and others depending on the tumour type).
- Urinalysis.
- Performance Status (ECOG Performance Status) (Annex 3).
- Concomitant medication.
- Echocardiogram/MUGA.
- Thoracic, abdominal, and pelvic CT scan (bone scan).
- Extraction of peripheral blood sample (biomarker analysis in blood).
- Tumour block for diagnosis of well- or moderately differentiated neuroendocrine tumour for biomarker analysis.

Patients should start the study treatment within two working days following the baseline visit.

11.3 Day 1 visit (may occur on the same day as the baseline visit if all baseline visit test results are available).

- Confirm that all the screening period and baseline visit procedures have been carried out.
- Confirm that the patient meets the inclusion criteria and none of the exclusion criteria.
- Instruct the patient regarding the administration of the study medication and provide the study medication for a complete cycle, i.e., 28 days.

11.4 Treatment Visit

- Days 1, 8, 15 and 22 of each cycle:
 - Physical examination.
 - Signs and symptoms.
 - ECOG performance status.
 - Vital signs (blood pressure, heart rate, temperature, height and weight). Recalculate body surface area if the variation has been shown to be greater than 10%.
 - Complete blood test (See schedule of assessments, Annex I).
 - Recording of adverse events.
 - Recording of concomitant medication.
 - Accounting for medication.
 - Administration of the study intravenous medication (TH-302 is not administered on D1 or on D15) and dispensation of oral medication.

- Visit every 8 weeks (from D1 C1 onwards):
 - NET markers (chromogranin A, enolase 1 and others depending on the tumour type) (+/- 1 week).
 - Thoracic, abdominal, and pelvic CT scan reassessment (+/- 1 week).
 - If reassessing via bone scan, perform every 24 weeks.

These procedures will not be postponed in the event of cycle delays and must be performed every 8 weeks until disease progression, regardless of whether the patient has completed the treatment.

11.5 End-of-Study Treatment Visit

This visit will take place once disease progression has been identified, in the event of unacceptable toxicity or if the patient decides to withdraw their consent to continue in the study. The end of treatment visit must take place 4 weeks after concluding treatment, irrespective of the cause of treatment discontinuation.

The following procedures will be performed:

- Physical examination.
- Signs and symptoms.
- ECOG performance status.
- Complete blood test (See schedule of assessments, Annex I).
- NET markers (chromogranin A, enolase 1 and others depending on the tumour type).
- Urinalysis.
- Echocardiogram/MUGA.
- Recording of adverse events.
- Recording of concomitant medication.
- 12-lead ECG (only if clinically indicated).
- Thoracic, abdominal, and pelvic CT scan (if applicable).
- Bone scan, if clinically indicated.
- Drug accountability.

11.6 Follow-up

The following procedures will be performed during follow-up until disease progression:

- ECOG performance status.
- Thoracic, abdominal, and pelvic CT scan and/or bone scan (if applicable).
- Cancer treatment received.

Tumour assessment must be performed every 8 +/- 1 weeks until disease progression, irrespective of whether the patient has completed the treatment.

After disease progression, the overall survival secondary endpoint will be performed following the site's usual practices (in terms of scheduling visits), and must be continued until death or end of the trial, whichever occurs first.

12. ETHICAL ASPECTS

12.1. Legal Considerations

This clinical study will be conducted in accordance with the protocol, the principles established in the latest revised version of the Declaration of Helsinki (Annex 5) and in accordance with applicable regulatory legislation, in particular, the ICH harmonised tripartite guideline on good clinical practice 1996 and Royal Decree 223/2004 on Clinical Trials, regulating clinical trials with medicinal products in Spain, which incorporates the whole of European Directive 2001/20/EC on the approximation of provisions of the Member States relating to the implementation of GCP in the conduct of clinical trials on medicinal products for human use.

12.2. Patient's Informed Consent

Before the screening assessment, the patient will be informed about the nature of the study drug and will receive the relevant information concerning the purpose of the study, the potential benefits and potential adverse events. The patient will be informed of the procedures to be undertaken and the potential risks to which he/she could potentially be exposed.

Then, the patient (or, in the case of disabled patients, his/her legal representative) must read (or be informed orally before witnesses) and sign two copies of the informed consent form that will have previously been approved. The patient will receive a signed copy of the informed consent form. The patient may withdraw from the study at any time without it affecting his/her ongoing medical care. Verification that the patient has given written informed consent will be recorded in the patient's CRF.

12.3. Respect for Confidentiality

The investigator will be responsible for storing the appropriate information about each patient (for example, name, address, telephone number, social security number and study ID number) so that the health authorities may have access to said information if necessary. These records shall be kept confidential for as long as required by local legislation.

The highest levels of professional conduct and confidentiality will be maintained at all times, ensuring compliance with national data protection legislation.

The patient's identity in the study documents will be coded, and authorised personnel, the sponsor, the study monitor, and the investigator's staff at each site will have access to personal details that could identify the patient if required for the data verification processes. The patient study codes will be assigned by the study sponsor through the monitor, and will be created by assigning a unique identity number to each patient enrolled in the study. These codes will be safeguarded by the study sponsor and monitor. Personal details that could identify the patient will be kept confidential.

12.4. Liability Insurance

The sponsor has taken out an insurance policy to cover the liability of the investigator and other parties participating in the study:

A phase II trial to assess the activity and safety of TH-302 in combination with sunitinib in patients

Insurance Company:

[REDACTED]

[REDACTED]

13. STUDY DOCUMENTATION

13.1 Files

The investigator must maintain adequate and accurate records to ensure that the study is fully documented and to allow the study data to be subsequently checked. These documents are:

- Copies of completed CRFs, informed consent forms and the source documents.
- Investigator's file containing the protocol and any amendments, investigational medicinal product information as well as copies of essential documents.
- Records related to the investigational medicinal product(s).

In addition, all original source documents supporting CRF entries must be readily available.

The patients' original medical documentation would include the patients' hospital/medical records, doctors'/nurses' notes, the appointment book, original laboratory reports, ECG, EEG, X-ray, pathology and special assessment reports, signed informed consent forms, letters from specialists and patients' screening and enrolment forms.

13.2 Case Report Form

The principal investigator or a study team authorised representative must complete and sign an electronic CRF for each patient enrolled in the study. This also applies to patients who do not complete the study (even during the screening period prior to enrolment, if completion of a CRF has been started). If a patient withdraws from the study, the reason must be indicated in the CRF. If a patient withdraws due to a treatment-limiting adverse event, every effort should be made to clearly document the result.

The database will be managed to allow the eCRF to generate further information requests that the investigator will be obliged to answer by confirming or modifying the data asked about. The requests, with their responses, will be managed through the eCRF. The eCRF must be kept up-to-date in order to allow the monitor to review the patients' status during the course of the study. Procedures and controls will be employed to ensure the confidentiality of electronic records.

13.3 Monitoring

The study will be monitored by the company MFAR. The accuracy of data collected in the CRFs shall be guaranteed by the monitor by verifying the data recorded in the CRF against data recorded in the medical record or in other documents such as laboratory reports, images, drug dispensation records, or any other source document containing information regarding the progression and follow-up of patients during their participation in the study.

Data to be verified shall be set out in the data verification plan, drawn up by the monitor and approved by the sponsor. The planned frequency of monitoring for each site will also be established.

To ensure data accuracy, precision and completeness, GETNE:

- Will provide the material with the necessary information to properly coordinate the study procedures.
- Will provide a training session for the investigator's team that will include a review of the protocol, the completion of the eCRF and study procedures.
- Will conduct regular site visits to review study progress, investigator and patient compliance with procedures and to address any urgent problems.
- Will remain in contact with the site for any query via e-mail, phone and/or fax.
- Will review and evaluate the CRF entries to detect any possible errors.
- Will ensure the quality of the data.

To ensure data accuracy for the safety of the patient, the investigator must include the original laboratory reports, imaging tests, medical reports and medical notes taken at each visit.

13.4.- *Publication of results*

The sponsor undertakes to promptly disseminate the results through the usual scientific means (conferences and publications), under the responsibility of the scientific coordinator and translational study coordinator. The study coordinator reserves the right to select his/her position in the different publications and reports that the study may envisage. The translational study coordinator will hold an assured position amongst the study authors. The remaining positions will be assigned to the participating investigators according to a rigorous order of recruitment.

ANNEX 1. SCHEDULE OF ASSESSMENTS

	Screening (28 days)	Cycles				End of treatment (at 4 weeks +/- 1) after the end of treatment	Follow-up until progression (every 8 weeks until progression)	Post- progression follow-up
		Day 1 (D1)	Week 2 (D8)	Week 3 (D15)	Week 4 (D22)			
Informed consent ¹	X							
Inclusion/exclusion criteria	X							
Medical record and demographic data ²	X							
Physical examination (weight, height and vital signs)	X	X	X	X	X	X	X	
Signs/symptoms		X	X	X	X	X	X	
ECOG performance status ^(Annex 3)	X	X	X	X	X	X	X	
Haematology and haemostasis ⁴	X	X	X	X	X	X	X	
Full clinical chemistry ⁵	X	X	X	X	X	X	X	
NET markers ⁶	X	Every 8 weeks from D1C1 until progression and end of treatment visit.						
Pregnancy test ⁷	X ≤ 7 days)							
12-lead ECG ⁸	X		X ⁸		X ⁸			
Urinalysis	X					X		
Echocardiogram/MUGA ⁹	X					X		
Recording of adverse events	X	X	X	X	X	X	X	
Recording of concomitant medication	X	X	X	X	X	X	X	
Sunitinib dispensation record		X						
Dose record/sunitinib compliance		X	X	X	X			
TH-302 administration			X		X			
CT image tumour measurements ¹⁰	X	Every 8 weeks from D1C1 until progression and end of treatment visit.						
Collection and freezing of blood sample for marker tests ¹¹	X							
Shipment of tumour sample for marker tests ¹²	X							
Post-study survival ¹³								X

1. Patients will be required to sign two copies of the informed consent form. The patient must indicate his/her degree of consent with respect to the use of biological samples.
2. Medical record and demographic data: Includes but is not limited to: specific cancer history, date of diagnosis, type of primary tumour with histological diagnosis, previous surgical procedures and dates, and any other relevant medical history within the last 6 months.
3. Physical examination: weight, height, body surface area and vital signs: heart rate, blood pressure, body temperature.
4. Haematology and haemostasis: haematocrit, haemoglobin, platelet count, white blood cell count, red blood cell count, neutrophil count and lymphocyte count. Coagulation will include prothrombin time (PT), the international normalised ratio (INR) and activated partial thromboplastin time (APTT). This will be conducted at the baseline visit (≤ 7 days) and at each pre-treatment visit (± 3 days prior to day 8 and ± 1 day prior to day 22 of each cycle). It will also be conducted ± 1 day prior to day 15 to ensure a weekly follow-up of the patients.
5. Clinical chemistry: AST, ALT, GGT, alkaline phosphatase, direct and total bilirubin, urea, calcium, chloride, creatinine, glucose, LDH, phosphorus, magnesium, potassium, sodium, albumin at the baseline visit (≤ 7 days) and at each pre-treatment visit (± 3 days prior to day 8 and ± 1 day prior to day 22 of each cycle). It will also be conducted ± 1 day prior to day 15 to ensure a weekly follow-up of the patients.
6. Enolase 1, chromogranin A (or peptide secreted functionally) tumour markers at baseline visit, every 8 weeks (± 1 week) and at the end-of-study visit.
7. Urine and blood pregnancy test in female patients of childbearing age. This will be conducted within 7 days prior to the day 1 visit and whenever pregnancy is suspected.
8. 12-lead electrocardiogram: before every test, the subject must be at rest for approximately 10 minutes. The subject should be in a semi-lying or supine position; the same position must be adopted for all subsequent ECG tests.
In the first cycle, an ECG will be performed at day 8 and at day 22 immediately after completion of the TH-302 infusion. Thereafter, an ECG will be performed at the discretion of the investigator
9. Baseline and end-of-study visit echocardiogram, and if clinically indicated.
10. Thoracic, abdominal, and pelvic CT scan within 28 days prior to study enrolment and subsequently every 8 ± 1 weeks and at the end-of-study visit. For tumour reassessments, the same exploratory technique used in the baseline examination must be adopted. A baseline bone scan may be performed within 28 days prior to day 1 of the first cycle, if there is a clinical suspicion of bone metastases. In the event of bone metastases, a reassessment bone scan will be performed every 12 weeks until week 24 and thereafter every 24 weeks until the end of treatment. Margin of ± 14 days with reference to the scheduled visit.
An MRI may only be performed in exceptional circumstances and only in cases when a CT scan is not possible.
11. Blood sample for the analysis of genetic markers that will be sent to [REDACTED]. Only the tubes from the baseline visit will be sent.

A phase II trial to assess the activity and safety of TH-302 in combination with sunitinib in patients

12. Paraffin-embedded tumour sample for marker analysis that will be sent to [REDACTED]
[REDACTED]

13. Determination of overall survival of patient (living/death/lost to follow-up). According to the site's usual practices, until the end of the trial.

ANNEX 2. WORLD HEALTH ORGANIZATION (WHO) CLASSIFICATION OF GASTROENTEROPANCREATIC NEUROENDOCRINE TUMOURS (GEP-NETs)

WHO	Tumour	Grade	Mitosis (10 HPF)	Ki67 index (%)
WHO 1	NET	G1	< 2	≤ 2
WHO 2	NET	G2	2-20	3-20
WHO 3	NEC	G3	> 20	> 20
	MANEC Tumour-like lesions			

WHO: World Health Organization; NET: Neuroendocrine tumour; NEC: Neuroendocrine carcinoma; HPF: High-power Fields.

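### Section 11.4 and Annex 1 of the protocol give different bone-scan schedules and stopping points, so progression seen only on bone scan can be dated differently from site to site

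*Protocol*

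**What the plan says.** Three places in the protocol govern repeat bone imaging.

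- Section 11.4 (Treatment Visit), in the list of procedures counted from day 1 of cycle 1: "If reassessing via bone scan, perform every 24 weeks". The paragraph closing that list says the procedures are not postponed for cycle delays and "must be performed every 8 weeks until disease progression, regardless of whether the patient has completed the treatment".
- Annex 1, footnote 10, for patients with bone metastases: "a reassessment bone scan will be performed every 12 weeks until week 24 and thereafter every 24 weeks until the end of treatment". It then adds: "Margin of ± 14 days with reference to the scheduled visit". Section 11.4 gives no window for the bone scan.
- Section 11.6 (Follow-up) lists CT and/or bone scan, where applicable, among the procedures continued until progression, and adds: "Tumour assessment must be performed every 8 +/- 1 weeks until disease progression, irrespective of whether the patient has completed the treatment".

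Two further lines bear on the point. The end-of-treatment visit in section 11.5 includes "Bone scan, if clinically indicated". At baseline, footnote 10 makes the scan optional and ties it to suspected bone disease.

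Section 11.1 points to Annex 1 for the schedule but does not say that it overrides the text. The SAP repeats the endpoint definitions in section 1.5.2 and says nothing about bone-scan timing. The CT interval, 8 weeks with a 1-week margin, is the same in sections 11.4 and 11.6 and in Annex 1.

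**The concern.** A site cannot follow both texts. One that works from section 11.4 does no bone scan at week 12; one that works from the footnote does. A site using the footnote also has no scheduled bone scan after treatment stops, while sections 11.4 and 11.6 carry imaging on to progression. Section 6.2 keeps patients who stop for toxicity on the scheduled follow-up, so this second difference applies to real patients.

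PFS, time to progression and response duration all end at the first objective radiological progression (protocol section 10.1; SAP section 1.5.2), with death also counting for PFS and response duration. An event found only by imaging carries the date of the scan that showed it. If the scan dates depend on which page a site follows, so do the event dates, and the trial runs at 10 sites.

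**Working it through.** The plan states no figure to reproduce. The check sets the calendars side by side, taking weeks from day 1 of cycle 1.

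| | Section 11.4 | Annex 1, footnote 10 |
|---|---|---|
| Nominal bone-scan weeks | 24, 48, 72, 96, ... | 12, 24, 48, 72, 96, ... |
| Window | none given | 14 days either side |
| Stops at | progression | end of treatment |

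**Weeks that differ.** Listed out to week 144, the only week in one calendar and not the other is week 12. From week 24 the nominal weeks coincide.

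**Position against CT.** The week-12 bone window runs from 12 − 2 = 10 to 12 + 2 = 14 weeks. The neighbouring CT windows are weeks 7–9 and 15–17, so there is no overlap. From week 24 on, every scheduled bone scan falls on a nominal CT week.

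**Effect on dates.** Take progression visible only on bone scan in a patient still on treatment.

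- Arising in weeks 0–12: dated week 12 under the footnote and week 24 under section 11.4. Difference 24 − 12 = 12 weeks.
- Arising in weeks 12–24: dated week 24 under both. No difference.
- Arising later, on treatment: no difference in nominal dates.
- Arising after treatment stops without progression: no scheduled bone scan under the footnote; imaging continues under sections 11.4 and 11.6.

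**Scale, on an assumption.** The documents give no rate for such events. Assume an exponential time to bone-scan-only progression with median m, so that F(t) = 1 − exp(−t·ln 2/m).

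| Assumed median | F(12 weeks) | F(24 weeks) | F(12)/F(24) |
|---|---|---|---|
| 6 months | 0.273 | 0.471 | 0.58 |
| 11.4 months | 0.154 | 0.285 | 0.54 |
| 24 months | 0.077 | 0.147 | 0.52 |

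About 8% to 27% of patients with bone metastases would have such an event by week 12. Slightly more than half of the bone-scan-only events of the first 24 weeks would be dated 12 weeks apart under the two texts. These are shares within a subgroup of unknown size.

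**Confirmed response.** On scheduled CTs, the earliest response is week 8 and its earliest confirmation week 16. A bone lesion found at week 12 could prevent that confirmation; under section 11.4 the first bone re-scan comes 24 − 16 = 8 weeks after it. For scale, assume 10–20% of the 43 patients have bone metastases, 20% respond (the plan's response threshold), 8–27% have bone-scan-only progression by week 12, and these are independent:

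- low: 43 × 0.10 × 0.20 × 0.08 = 0.07 patients
- high: 43 × 0.20 × 0.20 × 0.27 = 0.46 patients

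Both are below one, even if every response appeared at week 8.

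**The case against.** The strongest reply is that the conflict is narrow. It concerns one on-treatment time point, only patients with bone metastases, and only findings that CT of thorax, abdomen and pelvis does not show. Inclusion criterion 7 requires measurable disease, and the CT schedule that drives response is consistent. All of that stands, and it limits the point to the dating of progression.

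It can also be said that the continuation sentence in section 11.4 speaks of 8-weekly procedures and may not have been meant for the bone scan. That has some force, but section 11.6 names bone scan in follow-up until progression, so the conflict over the stopping point does not rest on that sentence.

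Four stronger readings are tempting and are not supported.

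- A reader might infer that the response count, and with it the 8-responder rule, depends on which page a site follows. The expected number of reclassified responders above is below one under the stated assumptions, and the rule says only that development is likely to continue.
- Twelve weeks is 2.8 months, and 2.8/11.4 = 24% of the sunitinib median PFS that the protocol cites. That sets one patient's largest shift against another trial's median; it is not a shift in this trial's median PFS.
- A reader might infer that patients who stop treatment get no further bone scans. The footnote taken alone says so, but sections 11.5 and 11.6 list bone scan when indicated or applicable.
- The remark in section 5.1 that keeping to the assessment schedule is essential follows directly on the 8-weekly tumour assessment, which is not in conflict.

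**Conclusion.** The inconsistency is certain: two intervals before week 24, a window in one place only, and two stopping points, with no rule of precedence. It should be corrected, though it does not threaten the primary result. The largest on-treatment effect on any one patient is a 12-week nominal difference in the date of bone-scan-only progression arising by week 12. After treatment stops, such progression may be dated late or missed where a site follows the footnote. PFS, time to progression and response duration carry most of the effect. The total effect on the trial cannot be sized, because the documents state neither the proportion of patients with bone metastases nor how often progression shows on bone scan alone. The percentages and fractional patient counts above rest on assumed inputs and show scale only.

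**What to change.** Reconcile section 11.4, section 11.6 and footnote 10 to one bone-scan calendar and one window, applied at all sites. In the footnote, replace the end of treatment with disease progression as the point at which bone scans stop, to match sections 11.4 and 11.6 and the PFS and time-to-progression definitions.

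The documents do not show which interval before week 24 was intended, so the sponsor has to decide that. Moving the early bone scan to a CT visit, for example week 16 in place of week 12, is an option. It is not a correction, since neither text contains it and a bone scan between CT visits is not in itself an error.

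The cost is a wording amendment and a few off-treatment bone scans in patients with bone metastases who stop before progression. The change leaves the optional baseline scan as it is, so bone disease that goes unsuspected and is not seen on CT would still not be followed.
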